**Same shell as Table 14.2.1.1.1**

**Programming Note:** Continue for all parameters. Parameters include: Head Tremor, Face (including jaw) Tremor, Voice Tremor, Upper Limb Tremor: Forward Outstretched Postural Tremor-Right, Upper Limb Tremor: Forward Outstretched Postural Tremor-Left, Upper Limb Tremor: Lateral Wing Beating Postural Tremor-Right, Upper Limb Tremor: Lateral Wing Beating Postural Tremor-Left, Upper Limb Tremor: Kinetic Tremor-Right, Upper Limb Tremor: Kinetic Tremor-Left, Lower Limb Tremor: Extended-Right, Lower Limb Tremor: Extended-Left, Lower Limb Tremor: Heel-Shin-Right, Lower Limb Tremor: Heel-Shin-Left, Archimedes Spirals-Right, Archimedes Spirals-Left, Handwriting, Dot Approximation Task-Right, Dot Approximation Task-Left, and Standing Tremor. Change from Screening should only be presented after the baseline visit.

Table 14.2.1.2.1  
Summary of Central Rater TETRAS-PS Upper Limb Subscale Scores by Study Visit  
FAS and Per-Protocol Population

**Same shell as Table 14.2.1.1.1**

**Programming Note:** Parameter will be TETRAS-PS Upper Limb Subscale Score, Upper Limb Tremor: Forward Outstretched Postural Tremor-Right, Upper Limb Tremor: Forward Outstretched Postural Tremor-Left, Upper Limb Tremor: Lateral Wing Beating Postural Tremor-Right, Upper Limb Tremor: Lateral Wing Beating Postural Tremor-Left, Upper Limb Tremor: Kinetic Tremor-Right, Upper Limb Tremor: Kinetic Tremor-Left, Archimedes Spirals-Right, Archimedes Spirals-Left, Handwriting, Dot Approximation Task-Right, and Dot Approximation Task-Left. Update footnote to read "The TETRAS Upper limb subscale score is the sum of the item 4, item 6, item 7 and item 8 scores (forward outstretched postural tremor, lateral "wing beating" postural tremor, kinetic tremor, Archimedes spirals, and dot approximation task from both sides of the body, as well as handwriting. The upper limb individual item question scores for each side of the body range from 0 to 4, with higher scores indicating more tremors. A negative change indicates improvement."

Commercially Confidential Information

Table 14.2.1.2.3  
Correlation between Central and Local TETRAS-PS Upper Limb Subscale Scores by Study Visit  
FAS and Per-Protocol Population

**Same shell as Table 14.2.1.1.4**

**Programming Note:** Update footnote to read "The TETRAS Upper limb subscale score is the sum of the item 4, item 6, item 7 and item 8 scores (forward outstretched postural tremor, lateral "wing beating" postural tremor, kinetic tremor, Archimedes spirals, and dot approximation task from both sides of the body, as well as handwriting. The upper limb individual item question scores for each side of the body range from 0 to 4, with higher scores indicating more tremors.)"

Table 14.2.1.2.4  
Summary of Local Rater TETRAS-PS Upper Limb Subscale Scores by Study Visit  
FAS and Per-Protocol Population

**Same shell as Table 14.2.1.1.1**

**Programming Note:** Parameter will be TETRAS-PS Upper Limb Subscale Score, Upper Limb Tremor: Forward Outstretched Postural Tremor-Right, Upper Limb Tremor: Forward Outstretched Postural Tremor-Left, Upper Limb Tremor: Lateral Wing Beating Postural Tremor-Right, Upper Limb Tremor: Lateral Wing Beating Postural Tremor-Left, Upper Limb Tremor: Kinetic Tremor-Right, Upper Limb Tremor: Kinetic Tremor-Left, Archimedes Spirals-Right, Archimedes Spirals-Left, Handwriting, Dot Approximation Task-Right, and Dot Approximation Task-Left. Update footnote to read "The TETRAS Upper limb subscale score is the sum of the item 4, item 6, item 7 and item 8 scores (forward outstretched postural tremor, lateral "wing beating" postural tremor, kinetic tremor, Archimedes spirals, and dot approximation task from both sides of the body, as well as handwriting. The upper limb individual item question scores for each side of the body range from 0 to 4, with higher scores indicating more tremors. A negative change indicates improvement."

*Approximation Task-Left. Update footnote to read “The TETRAS Upper limb subscale score is the sum of the item 4, item 6, item 7 and item 8 scores (forward outstretched postural tremor, lateral “wing beating” postural tremor, kinetic tremor, Archimedes spirals, and dot approximation task from both sides of the body, as well as handwriting. The upper limb individual item question scores for each side of the body range from 0 to 4, with higher scores indicating more tremors. A negative change indicates improvement.”*

Table 14.2.1.3.1  
Summary of Central Rater TETRAS-PS Upper Limb Tremor (Item 4) Scores by Study Visit  
FAS and Per-Protocol Population

**Same shell as Table 14.2.1.1.1**

**Programming Note:** Parameters will be TETRAS-PS Upper Limb Tremor (Item 4) Score, Upper Limb Tremor: Forward Outstretched Postural Tremor-Right, Upper Limb Tremor: Forward Outstretched Postural Tremor-Left, Upper Limb Tremor: Lateral Wing Beating Postural Tremor-Right, Upper Limb Tremor: Lateral Wing Beating Postural Tremor-Left, Upper Limb Tremor: Kinetic Tremor-Right, Upper Limb Tremor: Kinetic Tremor-Left. Update footnote to read "The TETRAS-PS Upper Limb Tremor (Item 4) Total score is the sum of the 6 item 4 scores (forward outstretched postural tremor, lateral "wing beating" postural tremor, and kinetic tremor scores) from both sides of the body, as well as handwriting. The upper limb individual item question scores for each side of the body range from 0 to 4, with higher scores indicating more tremors. A negative change indicates improvement."

Table 14.2.1.3.2  
Correlation between Central and Local TETRAS-PS Upper Limb Tremor (Item 4) Scores by Study Visit  
FAS and Per-Protocol Population

**Same shell as Table 14.2.1.1.4**

**Programming Note:** Update footnote to read "The TETRAS-PS Upper Limb Tremor (Item 4) Total score is the sum of the 6 item 4 scores (forward outstretched postural tremor, lateral "wing beating" postural tremor, and kinetic tremor scores) from both sides of the body. The upper limb individual item question scores for each side of the body range from 0 to 4, with higher scores indicating more tremors."

Table 14.2.1.3.3  
Summary of Local Rater TETRAS-PS Upper Limb Tremor (Item 4) Scores by Study Visit  
FAS and Per-Protocol Population

**Same shell as Table 14.2.1.1.1**

**Programming Note:** Parameters will be TETRAS-PS Upper Limb Tremor (Item 4) Score, Upper Limb Tremor: Forward Outstretched Postural Tremor-Right, Upper Limb Tremor: Forward Outstretched Postural Tremor-Left, Upper Limb Tremor: Lateral Wing Beating Postural Tremor-Right, Upper Limb Tremor: Lateral Wing Beating Postural Tremor-Left, Upper Limb Tremor: Kinetic Tremor-Right, Upper Limb Tremor: Kinetic Tremor-Left. Update footnote to read "The TETRAS-PS Upper Limb Tremor (Item 4) Total score is the sum of the 6 item 4 scores (forward outstretched postural tremor, lateral "wing beating" postural tremor, and kinetic tremor scores) from both sides of the body, as well as handwriting. The upper limb individual item question scores for each side of the body range from 0 to 4, with higher scores indicating more tremors. A negative change indicates improvement."

Commercially Confidential Information

Table 14.2.5.1  
Summary of In-Clinic Wearable Sensor (Kinesia) by Study Visit  
FAS and Per-Protocol Population

**Same Shell as Table 14.2.1.1.1**

Parameter: Kinesia Score, Side: Right, Task: Extended Arms Posture

Study Visit Statistic	Full Analysis Set			Per-Protocol Population		
	Protocol Amendment 1.0 (N=XX)	Protocol Amendment 2.0 or 3.0 (N=XX)	Overall (N=XX)	Cohort-1 (N=XX)	Protocol Amendment 2.0 or 3.0 (N=XX)	Overall (N=XX)

**Programming Note:** Remove footnote describing TETRAS-PS. Update SOURCE: to Listing 16.2.6.6.1. Continue for all study days and the following:

Parameter: Kinesia Score, Side: Right, Task: Wing-beating posture,

Parameter: Kinesia Score, Side: Right, Task: Kinetic "finger-to-chin" Movement,

Parameter: Kinesia Score, Side: Right, Task: Arm on Table Posture

Parameter: Kinesia Score, Side: Left, Task: Extended Arms Posture,

Parameter: Kinesia Score, Side: Left, Task: Wing-beating Posture,

Parameter: Kinesia Score, Side: Left, Task: Kinetic "finger-to-chin" Movement,

Parameter: Kinesia Score, Side: Left, Task: Arm on Table Posture

Parameter: Tremor Amplitude, Side: Right, Task: Extended Arms Posture,

Parameter: Tremor Amplitude, Side: Right, Task: Wing-beating Posture,

Parameter: Tremor Amplitude, Side: Right, Task: Kinetic "finger-to-chin" Movement,

Parameter: Tremor Amplitude, Side: Right, Task: Arm on Table Posture

Parameter: Tremor Amplitude, Side: Left, Task: Extended Arms Posture,

Parameter: Tremor Amplitude, Side: Left, Task: Wing-beating Posture,

Parameter: Tremor Amplitude, Side: Left, Task: Kinetic "finger-to-chin" Movement,

Parameter: Tremor Amplitude, Side: Left, Task: Arm on Table Posture

Parameter: Tremor Frequency, Side: Right, Task: Extended Arms Posture,

Parameter: Tremor Frequency, Side: Right, Task: Wing-beating Posture,

Parameter: Tremor Frequency, Side: Right, Task: Kinetic "finger-to-chin" Movement,

Parameter: Tremor Frequency, Side: Right, Task: Arm on Table Posture

Parameter: Tremor Frequency, Side: Left, Task: Extended Arms Posture,

Parameter: Tremor Frequency, Side: Left, Task: Wing-beating Posture,

Parameter: Tremor Frequency, Side: Left, Task: Kinetic "finger-to-chin" Movement,

Parameter: Tremor Frequency, Side: Left, Task: Arm on Table Posture

Parameter: Finger-Chin-Finger Quality, Side: Right, Task: Extended Arms Posture,

Parameter: Finger-Chin-Finger Quality, Side: Right, Task: Wing-beating Posture,

Parameter: Finger-Chin-Finger Quality, Side: Right, Task: Kinetic "finger-to-chin" Movement,

Parameter: Finger-Chin-Finger Quality, Side: Right, Task: Arm on Table Posture

Parameter: Finger-Chin-Finger Quality, Side: Left, Task: Extended Arms Posture,

Parameter: Finger-Chin-Finger Quality, Side: Left, Task: Wing-beating Posture,

Parameter: Finger-Chin-Finger Quality, Side: Left, Task: Kinetic "finger-to-chin" Movement,

Parameter: Finger-Chin-Finger Quality, Side: Left, Task: Arm on Table Posture

Commercially Confidential Information

Commercially Confidential Information

Table 14.3.1.1  
Summary of Adverse Events  
Safety Population

Category	Cohort-1 (N=XX)		Cohort-2 (N=XX)		Overall (N=XX)	
	Subjects n (%)	Events	Subjects n (%)	Events	Subjects n (%)	Events
Subjects with at least 1 TEAE	XX (XX.X%)	XX	XX (XX.X%)	XX	XX (XX.X%)	XX
Maximum Severity of TEAE						
Mild	XX (XX.X%)	XX	XX (XX.X%)	XX	XX (XX.X%)	XX
Moderate	XX (XX.X%)	XX	XX (XX.X%)	XX	XX (XX.X%)	XX
Severe	XX (XX.X%)	XX	XX (XX.X%)	XX	XX (XX.X%)	XX
Subjects with a Related TEAE [1]	XX (XX.X%)	XX	XX (XX.X%)	XX	XX (XX.X%)	XX
Subjects with a TEAE Leading to Discontinuation of Study Drug	XX (XX.X%)	XX	XX (XX.X%)	XX	XX (XX.X%)	XX
Subjects with an AE leading to Death	XX (XX.X%)	XX	XX (XX.X%)	XX	XX (XX.X%)	XX
Subjects with at least 1 SAE	XX (XX.X%)	XX	XX (XX.X%)	XX	XX (XX.X%)	XX
Maximum Severity of SAE						
Mild	XX (XX.X%)	XX	XX (XX.X%)	XX	XX (XX.X%)	XX
Moderate	XX (XX.X%)	XX	XX (XX.X%)	XX	XX (XX.X%)	XX
Severe	XX (XX.X%)	XX	XX (XX.X%)	XX	XX (XX.X%)	XX
Subjects with a Related SAE [1]	XX (XX.X%)	XX	XX (XX.X%)	XX	XX (XX.X%)	XX
Subjects with a SAE Leading to Discontinuation of Study Drug	XX (XX.X%)	XX	XX (XX.X%)	XX	XX (XX.X%)	XX
Subjects with an SAE leading to Death	XX (XX.X%)	XX	XX (XX.X%)	XX	XX (XX.X%)	XX

Abbreviations: TEAE = treatment emergent adverse event; SAE = serious adverse event.

Note: Percentages are n/Number of subjects in the Safety Population and respective Protocol Amendment\*100. AEs were coded using MedDRA version 21.1. A TEAE is any AE that occurs after the time of treatment with the study agent. Events meeting this definition will be those events that are a change from the subject's baseline conditions, including an increase in frequency or severity.

[1] Related TEAEs are those marked as Possibly Related, Probably Related, or Definitely Related on the case report form.

SOURCE: Listing 16.2.7

Table 14.3.1.2  
Incidence of Treatment Emergent Adverse Events by SOC and PT  
Safety Population

System Organ Class Preferred Term	Cohort-1 (N=XX)		Cohort-2 (N=XX)		Overall (N=XX)	
	Subjects n (%)	Events	Subjects n (%)	Events	Subjects n (%)	Events
Subjects with at least 1 TEAE	XX (XX.X%)	XX	XX (XX.X%)	XX	XX (XX.X%)	XX
System Organ Class 1	XX (XX.X%)	XX	XX (XX.X%)	XX	XX (XX.X%)	XX
Preferred Term 1	XX (XX.X%)	XX	XX (XX.X%)	XX	XX (XX.X%)	XX
Preferred Term 2	XX (XX.X%)	XX	XX (XX.X%)	XX	XX (XX.X%)	XX
Preferred Term 3	XX (XX.X%)	XX	XX (XX.X%)	XX	XX (XX.X%)	XX
System Organ Class 1	XX (XX.X%)	XX	XX (XX.X%)	XX	XX (XX.X%)	XX
Preferred Term 1	XX (XX.X%)	XX	XX (XX.X%)	XX	XX (XX.X%)	XX
Preferred Term 2	XX (XX.X%)	XX	XX (XX.X%)	XX	XX (XX.X%)	XX
Preferred Term 3	XX (XX.X%)	XX	XX (XX.X%)	XX	XX (XX.X%)	XX

Abbreviations: PT = preferred term; SOC = system organ class; TEAE = treatment emergent adverse event.

Note: Percentages are n/Number of subjects in the Safety Population and respective Protocol Amendment \* 100.

AEs were coded using MedDRA version 21.1.

A TEAE is any AE that occurs after the time of treatment with the study agent. Events meeting this definition will be those events that are a change from the subject's baseline conditions, including an increase in frequency or severity.

Subjects are counted once for each SOC and once for each PT. AEs are displayed by descending frequency of SOC, then PT within SOC, and then alphabetically by PT.

SOURCE: Listing 16.2.7

**Programming note:** SOC & PT text should be in title case in table, as shown in the shell. Ensure correct MedDRA version is printed in footnote.

Table 14.3.1.3  
Incidence of Treatment Emergent Adverse Events by SOC, PT, and Maximum Severity  
Safety Population

System Organ Class Preferred Term Maximum Severity	Cohort-1 (N=XX)		Cohort-2 (N=XX)		Overall (N=XX)	
	Subjects n (%)	Events	Subjects n (%)	Events	Subjects n (%)	Events
Subjects with at least 1 TEAE	XX (XX.X%)	XX	XX (XX.X%)	XX	XX (XX.X%)	XX
Any Event (Total)						
Mild	XX (XX.X%)	XX	XX (XX.X%)	XX	XX (XX.X%)	XX
Moderate	XX (XX.X%)	XX	XX (XX.X%)	XX	XX (XX.X%)	XX
Severe	XX (XX.X%)	XX	XX (XX.X%)	XX	XX (XX.X%)	XX
System Organ Class 1						
Any Event (Total)						
Mild	XX (XX.X%)	XX	XX (XX.X%)	XX	XX (XX.X%)	XX
Moderate	XX (XX.X%)	XX	XX (XX.X%)	XX	XX (XX.X%)	XX
Severe	XX (XX.X%)	XX	XX (XX.X%)	XX	XX (XX.X%)	XX
Preferred Term 1						
Mild	XX (XX.X%)	XX	XX (XX.X%)	XX	XX (XX.X%)	XX
Moderate	XX (XX.X%)	XX	XX (XX.X%)	XX	XX (XX.X%)	XX
Severe	XX (XX.X%)	XX	XX (XX.X%)	XX	XX (XX.X%)	XX

Abbreviations: PT = preferred term; SOC = system organ class; TEAE = treatment emergent adverse event.

Note: Percentages are n/Number of subjects in the Safety Population and respective Protocol Amendment \*100.

AEs were coded using MedDRA version 21.1.

A TEAE is any AE that occurs after the time of treatment with the study agent. Events meeting this definition will be those events that are a change from the subject's baseline conditions, including an increase in frequency or severity.

Subjects are counted once for each SOC and once for each PT.

The severity shown is the greatest severity reported for a particular subject (Severe > Moderate > Mild). AEs with a missing severity were counted as Severe.

AEs are displayed by descending frequency of SOC, then PT within SOC, and then alphabetically by PT.

SOURCE: Listing 16.2.7

**Programming note:** SOC & PT text should be in title case in table, as shown in the shell. Ensure correct MedDRA version is printed in footnote.

Table 14.3.1.4  
Incidence of Treatment Emergent Adverse Events by SOC, PT, and Relationship  
Safety Population

System Organ Class Preferred Term Relationship	Cohort-1 (N=XX)		Cohort-2 (N=XX)		Overall (N=XX)	
	Subjects n (%)	Events	Subjects n (%)	Events	Subjects n (%)	Events
Subjects with at least 1 TEAE	XX (XX.X%)		XX (XX.X%)		XX (XX.X%)	
Any Event (Total)						
Related	XX (XX.X%)	XX	XX (XX.X%)	XX	XX (XX.X%)	XX
Not Related	XX (XX.X%)	XX	XX (XX.X%)	XX	XX (XX.X%)	XX
System Organ Class 1						
Any Event (Total)						
Related	XX (XX.X%)	XX	XX (XX.X%)	XX	XX (XX.X%)	XX
Not Related	XX (XX.X%)	XX	XX (XX.X%)	XX	XX (XX.X%)	XX
Preferred Term 1						
Related	XX (XX.X%)	XX	XX (XX.X%)	XX	XX (XX.X%)	XX
Not Related	XX (XX.X%)	XX	XX (XX.X%)	XX	XX (XX.X%)	XX

Abbreviations: CRF = case report form; PT = preferred term; SOC = system organ class; TEAE = treatment emergent adverse event.

Note: Percentages are n/Number of subjects in the Safety Population and respective Protocol Amendment \*100.

AEs were coded using MedDRA version 21.1.

A TEAE is any AE that occurs after the time of treatment with the study agent. Events meeting this definition will be those events that are a change from the subject's baseline conditions, including an increase in frequency or severity.

Subjects are counted once for each SOC and once for each PT.

Subjects are classified according to the strongest relationship if the subject reported one or more events. Related TEAEs are those marked as Possibly Related, Probably Related, or Definitely Related on the CRF. AEs with a missing relationship will be considered related for this summary.

AEs are displayed by descending frequency of SOC, then PT within SOC, and then alphabetically by PT.

SOURCE: Listing 16.2.7

**Programming note:** SOC & PT text should be in proper case in table, as shown in the shell. Ensure correct MedDRA version is printed in footnote.

Table 14.3.2.1  
Incidence of TEAEs Leading to Withdrawal of Study Drug by SOC and PT  
Safety Population

**Same shell as Table 14.3.1.2**

Table 14.3.2.2  
Incidence of Serious Adverse Events by SOC and PT  
Safety Population

**Same shell as Table 14.3.1.2**

*Programming note: Add SAE to abbreviations.*

Table 14.3.3.1  
Listing of Adverse Events Leading to Study Drug Discontinuation  
All Subjects

Subject ID	System Organ Class/ Preferred Term/ Verbatim Term	Start Date (Study Day) Start Time/ End Date (Study Day) End Time	Severity/ Relationship	Outcome/ Study Drug Action Taken/ Other Action Taken	TEAE?/ Serious?/ Criteria Met
XXXXXX	XXXXXXXXXXXXXXXXXXXX/ XXXXXXXXXXXXXXXXXX/ XXXXXXXXXXXXXXXXXX	DDMMYY/HH:MM (XX)/ DDMMYY/HH:MM (XX)	XXXXXXXXXX/ XXXXXXXXXX	XXXXXXXXXXXX/ XXXXXXXXXXXXXX/ XXXXXXXXXXXXXXXXXX	XX/ XXX/ XXXXXXXXXX
	XXXXXXXXXX/ XXXXXXXXXXXXXXXXXX/ XXXXXXXXXXXXXX	DDMMYY/HH:MM (XX)/ DDMMYY/HH:MM (XX)	XXXXXXXXXX/ XXXXXXXXXX	XXXXXXXXXXXXXX	XX/ XX
	XXXXXXXXXX/ XXXXXXXXXXXXXXXXXX/ XXXXXXXXXXXXXXXXXX	DDMMYY/HH:MM (XX)/ DDMMYY/HH:MM (XX)	XXXXXXXX/ XXXXXXXXXX	XXXXXXXXXXXXXX	XX/ XX

Abbreviation: TEAE = treatment emergent adverse event.

Note: Study day is calculated relative to the date of first dose. For pre-dose: study day= Start Date/ Stop Date – first dose date; For post-dose: study day= Start Date/ Stop Date – first dose date + 1.

AEs were coded using MedDRA version 21.1.

A TEAE is any AE that occurs after the time of treatment with the study agent. Events meeting this definition will be those events that are a change from the subject's baseline conditions, including an increase in frequency or severity.

**Programming note:** "Other Action Taken" will be either None, Medication Required, Relevant Procedure, or Other; if specify text is needed, concatenate "Relevant Procedure:" or "Other:" with the text. If Serious? Is Yes, concatenate all serious criteria marked as Yes with a semicolon. If no events meet the criteria for display, present "No events are reported." SOC & PT text should be in proper case in table, as shown in the shell. Ensure correct MedDRA version is printed in footnote.

Table 14.3.3.2  
Listing of Serious Adverse Events  
Safety Population

**Same shell as Table 14.3.3.1**

Table 14.3.3.3  
Listing of Deaths  
Safety Population

**Same shell as Table 14.3.3.1**

Table 14.3.4.1  
Abnormal Laboratory Results  
Safety Population

Subject ID	Treatment Received	Parameter (unit)	Study Visit	Date/Time of Assessment (Study Day)	Standard Results	Change from Baseline [1]	Reference Range [2]	Reference Range Flag	Lab Panel	Comments/Reason Not Done
XXXXXX	CAD-1883	Hemoglobin (unit)	XXXXXX	DDMMYY/HH:MM (X)	XX		XX - YY		XXXXXX	
			XXXXXX	DDMMYY/HH:MM (X)	XX	XX	XX - YY		XXXXXX	
			XXXXXX	DDMMYY/HH:MM (X)	XX	XX	XX - YY		XXXXXX	
			XXXXXX	DDMMYY/HH:MM (X)	XX	XX	XX - YY	XXX	XXXXXX	
			XXXXXX	DDMMYY/HH:MM (X)	XX	XX	XX - YY		XXXXXX	
			XXXXXX	DDMMYY/HH:MM (X)	XX	XX	XX - YY		XXXXXX	
			XXXXXX	DDMMYY/HH:MM (X)	XX	XX	XX - YY		XXXXXX	
			XXXXXX	DDMMYY/HH:MM (X)	ND				XXXXXX	
			XXXXXX	DDMMYY/HH:MM (X)	XX	XX	XX - YY		XXXXXX	XXXXXX

Abbreviations: AL = abnormal-low; AH = abnormal-high; CS = clinically significant; NCS = not clinically significant; ND = not done.

Note: Study day is calculated relative to the date of first dose of study drug. For pre-dose: study day= Start Date/ Stop Date – first dose date; For post-dose: study day= Start Date/ Stop Date – first dose date + 1.

If any parameter has an abnormal value, results for all study visits are presented.

[1] Baseline is the last observation recorded prior to the first dose of treatment.

[2] Reference range is used to identify potentially clinically significant laboratory values.

**Programming note:** update abbreviations to reflect actual data. If test was not done, set results to ND; make sure last column is populated accordingly. Do not display serum HCG results in this listing. For reference range flag, concatenate AL or AH with clinical significance like "XX-YY" (eg, AL-CS).

Table 14.3.5.1.1  
Summary of Hematology Laboratory Results by Study Visit  
Safety Population

Parameter: XXXXXXXXXXXXXXX

Study Visit Statistic	Cohort-1 (N=XX)	Cohort-2 (N=XX)	Overall (N=XX)
Screening			
n	XX	XX	XX
Mean (SD)	XX.X (XX.XX)	XX.X (XX.XX)	XX.X (XX.XX)
Median	XX.X	XX.X	XX.X
Min, Max	XX, XX	XX, XX	XX, XX
Baseline [1]			
n	XX	XX	XX
Mean (SD)	XX.X (XX.XX)	XX.X (XX.XX)	XX.X (XX.XX)
Median	XX.X	XX.X	XX.X
Min, Max	XX, XX	XX, XX	XX, XX
Day 1			
n	XX	XX	XX
Mean (SD)	XX.X (XX.XX)	XX.X (XX.XX)	XX.X (XX.XX)
Median	XX.X	XX.X	XX.X
Min, Max	XX, XX	XX, XX	XX, XX
Change from Baseline			
n	XX	XX	XX
Mean (SD)	XX.X (XX.XX)	XX.X (XX.XX)	XX.X (XX.XX)
Median	XX.X	XX.X	XX.X
Min, Max	XX, XX	XX, XX	XX, XX

[1] The baseline value for each variable is the last observation recorded prior to the first dose of treatment.

SOURCE: Listing 16.2.8.1.1

**Programming Note:** Continue all parameters for Day 7, Day 14, and Day 21. Sort alphabetically by parameter.

Table 14.3.5.1.2  
Shift from Baseline in Hematology Laboratory Results by Study Visit and Treatment  
Safety Population

Parameter: XXXXXXXX

Study Visit Category	Baseline [1] Cohort-1 (N=XX)				
	Low n (%)	Normal n (%)	High n (%)	Abnormal n (%)	Missing n (%)
Day 7					
Low	XX (XX.X%)	XX (XX.X%)	XX (XX.X%)	XX (XX.X%)	XX (XX.X%)
Normal	XX (XX.X%)	XX (XX.X%)	XX (XX.X%)	XX (XX.X%)	XX (XX.X%)
High	XX (XX.X%)	XX (XX.X%)	XX (XX.X%)	XX (XX.X%)	XX (XX.X%)
Abnormal	XX (XX.X%)	XX (XX.X%)	XX (XX.X%)	XX (XX.X%)	XX (XX.X%)
Missing	XX (XX.X%)	XX (XX.X%)	XX (XX.X%)	XX (XX.X%)	XX (XX.X%)
Day 14					
Low	XX (XX.X%)	XX (XX.X%)	XX (XX.X%)	XX (XX.X%)	XX (XX.X%)
Normal	XX (XX.X%)	XX (XX.X%)	XX (XX.X%)	XX (XX.X%)	XX (XX.X%)
High	XX (XX.X%)	XX (XX.X%)	XX (XX.X%)	XX (XX.X%)	XX (XX.X%)
Abnormal	XX (XX.X%)	XX (XX.X%)	XX (XX.X%)	XX (XX.X%)	XX (XX.X%)
Missing	XX (XX.X%)	XX (XX.X%)	XX (XX.X%)	XX (XX.X%)	XX (XX.X%)
Day 21					
Low	XX (XX.X%)	XX (XX.X%)	XX (XX.X%)	XX (XX.X%)	XX (XX.X%)
Normal	XX (XX.X%)	XX (XX.X%)	XX (XX.X%)	XX (XX.X%)	XX (XX.X%)
High	XX (XX.X%)	XX (XX.X%)	XX (XX.X%)	XX (XX.X%)	XX (XX.X%)
Abnormal	XX (XX.X%)	XX (XX.X%)	XX (XX.X%)	XX (XX.X%)	XX (XX.X%)
Missing	XX (XX.X%)	XX (XX.X%)	XX (XX.X%)	XX (XX.X%)	XX (XX.X%)

Note: Percentages are n/Number of subjects in the Safety Population and respective Protocol Amendment\*100.

[1] The baseline value for each variable is the last observation recorded prior to the first dose of treatment.

SOURCE: Listing 16.2.8.1.1

**Programming Note:** Continue all parameters, for Protocol Version: 2.0 or 3.0 and Overall as well as for Day 7, Day 14, and Day 21. Sort alphabetically by parameter.

Table 14.3.5.2.1  
Summary of Serum Chemistry Laboratory Results by Study Visit  
Safety Population

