#### **4.2 Exclusion Criteria**

Subjects who meet any of the following criteria will be excluded from participation in the study:

1. Prior or ongoing medical condition or any abnormal finding on the Screening visit physical exam, ECG, laboratory testing that, in the Investigator's opinion, could adversely affect the safety of the subject or the conduct of the study assessments.
2. Any neurological abnormality other than ET upon neurological exam, including dystonia, ataxia, or any other neurodegenerative disease, including multiple sclerosis or Parkinson's disease.
3. Commercially Confidential Information
4. Significant cognitive impairment or dementia that, in the opinion of the Investigator, would interfere with participation in the study.
5. Commercially Confidential Information
6. Commercially Confidential Information
7. An unstable thyroid condition that, per the Investigator's judgment based on medically significant abnormality of thyroid function testing at Screening. Note: an abnormal TSH level at Screening can be followed by reflex testing of thyroid hormones (T3, T4), if needed, per the Investigator's judgment.
8. History of, or evidence of psychogenic tremor at Screening.
9. Commercially Confidential Information
10. Commercially Confidential Information

11. History of anaphylaxis or hypersensitivity reactions to any of CAD-1883 excipients.
12. Alkaline phosphatase, aspartate aminotransferase (AST), and/or alanine aminotransferase (ALT) level  $>2.5 \times$  upper limit of normal (ULN) at Screening and/or at Baseline/Pre-dose.
13. Serum creatinine  $>120 \mu\text{mol/L}$  and/or creatinine clearance  $<60 \text{ mL/min}$  (according to Cockcroft-Gault formula) at Screening and/or at Baseline/Pre-dose.
14. Total bilirubin  $>2.0 \times$  ULN at Screening and/or at Baseline/Pre-dose. Note: isolated bilirubin  $>2.0 \times$  ULN is acceptable if bilirubin is fractionated and direct bilirubin is  $<35\%$ .
15. Exclusionary ECG abnormalities:
  - a. History of Long QT syndrome and/or QTcF (Fridericia's correction) interval  $>450 \text{ msec}$  (males) or  $>470 \text{ msec}$  (females) per 12-lead ECG done at Screening.

Commercially Confidential Information

16. Commercially Confidential Information

17. History of Alcohol Use Disorder per Diagnostic Statistical Manual of Mental Disorders, Fifth Edition (DSM-V) criteria.

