### **11.2.4 Sample Size Determination**

Approximately 30 subjects will be enrolled. No formal statistical power analysis was conducted. Each subject will be assessed for change from their own Baseline.

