 The subject should be instructed to self-administer their first daily dose of CAD-1883 4 to 5 hours prior to the scheduled and/or anticipated dosing of the second daily dose of CAD-1883. The second daily dose of CAD-1883 should be taken in the clinic 4 to 5 hours after the first daily dose.

 Commercially Confidential Information

 Commercially Confidential Information

 Commercially Confidential Information

 TETRAS Performance Subscale assessments at Screening, Baseline/Pre-dose, Days 1, 7, 14, and 21 will be recorded via videography for central rating.

 Screening: Commercially Confidential Information

 Performed between 2-4 hours following the second dose in the clinic.

 Performed between 2-4 hours following the second daily dose in the clinic.

 Wearable sensor measurement of upper-limb tremor will be captured once at the site, at any time during Screening and Day 21.

 Wearable sensor measurements of upper limb tremor will be captured at two different times during the Baseline/Pre-dose visit.

 Wearable sensor measurements of upper limb tremor will be captured once, 2 to 4 hours following the in-clinic dose. For Day 1, this is to be done 2-4 hours after the 2nd in-clinic dose.

 At the Baseline/Pre-dose visit, the “baseline” version of the C-SSRS will be administered. This version assesses Suicidal Ideation and Suicidal Behavior during the subject’s lifetime and during a predefined period. At the Day 21 visit (and the Early Termination visit for subjects withdrawing early), the “since last visit” version will be administered. The C-SSRS does not need to be completed at the Day 14 visit if it is not an Early Termination visit. During Early Termination visit, the subject will not receive study drug, will undergo all required procedures as well as the C-SSRS.

 Both doses of study drug are to be administered in the clinic with the second dose being administered 4-5 hours after the first.

 All laboratory collections on Days 1, 7, 14 should be performed after the TETRAS-PS assessment.

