#### **3.2. Sample Size and Power**

Up to 30 subjects will be enrolled. No formal statistical power analysis was conducted.

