## **9.2. Clinical Laboratory Evaluations**

Screening and safety laboratory tests will be performed at Screening, Pre-dose, Day 1, Day 7, Day 14, and at follow-up on Day 21. All laboratory test results will be summarized descriptively by study visit for the Safety Population overall and by cohort as both observed values and change from baseline values for each parameter. Categorical urinalysis results will be summarized using frequencies by study visit and cohort. Levels of composite biomarker panel for renal tubular injury will also be summarized by study visit and listed.

Shifts from baseline for clinical laboratory values below, within, or above the normal range will be provided for hematology and chemistry results by study visit. See Section 6.1.1 for the definition of baseline. Clinically significant abnormal findings will be reported as AEs. Abnormal laboratory results will be listed.

Pregnancy test results will be listed.

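### The laboratory shift tables have no category for the size of a rise, so an enzyme already High at entry stays High-to-High however far it climbs; separately, their shell leaves out Day 1.

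*SAP*

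**What the plan says.** SAP 9.2 lists laboratory tests at Screening, Pre-dose and Days 1, 7, 14 and 21, and then states: "Shifts from baseline for clinical laboratory values below, within, or above the normal range will be provided for hematology and chemistry results by study visit".

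The shell for this is Table 14.3.5.1.2 (hematology). Its rows and columns are Low, Normal, High, Abnormal and Missing. Its visits are Days 7, 14 and 21, and the programming note confirms them: "Continue all parameters, for Protocol Version: 2.0 or 3.0 and Overall as well as for Day 7, Day 14, and Day 21". The chemistry shift table, 14.3.5.2.2, holds the liver tests and borrows its shell from a Table 14.5.1.2, a number that is not in the SAP's list of planned tables. Table 14.3.5.1.2 is presumably meant. Quantitative urinalysis (14.3.5.3.2) reuses the hematology shell directly.

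The subject-level Table 14.3.4.1 carries the footnote "Reference range is used to identify potentially clinically significant laboratory values". Its flag joins abnormal-low or abnormal-high to a clinically significant / not clinically significant suffix. It has a change-from-baseline column and shows every visit of any parameter with an abnormal value.

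On entry, Protocol 4.2 criterion 12 excludes "Alkaline phosphatase, aspartate aminotransferase (AST), and/or alanine aminotransferase (ALT) level" only when above 2.5 × ULN. Criterion 14 does the same for total bilirubin above 2 × ULN, but its note accepts an isolated higher value when the direct fraction is below 35%.

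On the Day 1 sample, footnote 27 of the protocol's schedule says "All laboratory collections on Days 1, 7, 14 should be performed after the TETRAS-PS assessment". Protocol 8.1 puts that day's assessment 2 to 4 hours after the second in-clinic dose.

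**The concern.** Safety is the primary objective, and a shift table is where a reader looks for how many subjects worsened. A three-level coding has no room above High. Because the entry criteria allow High at baseline, the subjects with least reserve against a hepatic effect are the ones whose worsening the table cannot show. A trivial crossing of the limit, on the other hand, is counted.

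Elsewhere the SAP does tabulate by size: QTcF bands and increases (9.4), orthostatic falls (9.3), and a numeric threshold for the renal composite (Figure 14.5). The visible plan for routine chemistry has nothing comparable.

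The Day 1 gap is a separate inconsistency. Under the current protocol that sample follows both in-clinic doses, so it is the first on-drug laboratory result, and the shift tables leave it out.

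**Working it through.** The documents give no figure to reproduce here: laboratory data are descriptive, and Protocol 11.2.4 says "Approximately 30 subjects will be enrolled. No formal statistical power analysis was conducted".

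**1. What the shift coding can show.** Category = High if value / ULN > 1.

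| Baseline (× ULN) | Post-dose (× ULN) | Fold | Shift cell |
|---|---|---|---|
| 0.99 | 1.01 | 1.02 | Normal → High |
| 1.01 | 2.02 | 2 | High → High |
| 2.4 | 10 | 4.2 | High → High |
| 2.5 | 20 | 8 | High → High |
| 2.4 | 2.4 | 1 | High → High |

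The last four rows cannot be told apart.

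**2. What the continuous summary shows.** Table 14.3.5.2.1 uses the summary shell with mean, SD, median, minimum and maximum of change, Day 1 included. Take 30 subjects, one going from 2.5 to 10 × ULN and the rest unchanged:

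- mean change = 7.5 / 30 = 0.25 × ULN
- median = 0
- maximum = 7.5 × ULN

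So the rise is visible. If two subjects rose by 7.5, the mean would be 15 / 30 = 0.5, the median still 0 and the maximum still 7.5. The maximum shows the largest rise, not how many subjects had one or where they started.

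**3. Visits.** Post-dose laboratory visits in SAP 9.2: Days 1, 7, 14 and 21 (four). In the shift shell: Days 7, 14 and 21 (three). The hematology summary shell, 14.3.5.1.1, does include Day 1.

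**4. Chance out-of-range values.** Protocol Appendix B shows 23 chemistry analytes (total and direct bilirubin counted separately) and 13 hematology analytes, 36 in all; redacted analytes are not counted. Values = 36 × 4 visits × 30 subjects = 4,320. The chance rate per test is an assumption; the documents give none.

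| Assumed rate p | Expected flags, 4,320 × p | P(at least one per subject-visit), 1 − (1 − p)^36 |
|---|---|---|
| 1% | 43 | 30% |
| 2.5% | 108 | 60% |
| 5% | 216 | 84% |

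The expected count does not need independence between analytes. The last column does, and related pairs such as AST/ALT or hemoglobin/hematocrit make independence doubtful.

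**5. Effect of a ULN-multiple category.** For three enzymes, 3 × 4 × 30 = 360 values. With a 2.5% upper tail, 360 × 0.025 = 9.0 are expected above ULN by chance. Assume a lognormal with ULN at the 97.5th percentile and log-SD σ; then P(value > 2.5 × ULN) = 1 − Φ(1.96 + ln 2.5 / σ).

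- σ = 0.6: 0.000244 × 360 = 0.09
- σ = 0.3: 0.00000027 × 360 = 0.0001

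A count above 2.5 × ULN would therefore contain almost no chance values, apart from subjects who enter close to that limit.

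**The case against.** The strongest reply is that nothing is lost. A large rise appears as the maximum change in Table 14.3.5.2.1, for every visit in Table 14.3.4.1, and with percent change in the laboratory listings. Protocol 7.1 also requires a finding present at Screening that significantly worsens to be reported as an adverse event, which feeds the primary endpoint. That stands, and it rules out the stronger reading that such a rise would go unrecorded.

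A reader might also infer that chance values swamp the abnormal flag. The documents do not support this: the clinical-significance suffix is a second filter, and Table 14.3.4.1 is a subject-level display, so chance values inflate no incidence count there. The suffix does rest on investigator judgement in an open-label study, with no visible numeric criterion.

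Nor is it right that the Day 1 sample is never classified, since the range flag is displayed for it in Table 14.3.4.1, or that its absence from the shift shell causes the High-to-High masking, which comes from the coding alone. Renal injury is better served than the shift tables suggest: SAP 9.7, Tables 14.3.5.4.1 and 14.3.5.4.2 and Figure 14.5 give fold changes from Day 1 and a composite with a threshold of 1.18.

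Two more points stand. Entry limits are not offered anywhere as on-treatment thresholds, and splitting High at them alone would still hide 1.1 to 2.4 × ULN, or any further rise in a subject admitted under the bilirubin note. Some safety text is redacted, so only the visible plan can be judged.

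What the reply does not meet is that maxima and listings are not counts of subjects, and that the shell departs from SAP 9.2.

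**Conclusion.** The point holds as a gap in tabulation, not as a failure to capture data. The shift tables cannot separate a stable High value from one that rises several-fold, and no visible table counts subjects by size of rise. The Day 1 omission (one of four post-dose visits), the undefined 'Abnormal' level and the wrong chemistry shell reference are plain inconsistencies that need no assumption.

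How many subjects would be affected cannot be stated: the documents do not say how many enter with High values. The chance-flag figures (about 43 to 216 values) depend entirely on an assumed rate of 1% to 5% per test and are not a reason to redefine footnote [2] of Table 14.3.4.1. For a single-arm descriptive study of about 30 subjects this is a cheap improvement to the primary safety tabulation. It does not threaten the study's conclusions.

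**What to change.** 1. Add Day 1 to the shell of Table 14.3.5.1.2 and to its laboratory copies (14.3.5.2.2 and 14.3.5.3.2). Delete 'Abnormal' for numeric tests. In Table 14.3.5.2.2, change the shell reference from Table 14.5.1.2 to Table 14.3.5.1.2.

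2. For ALT, AST, ALP and total bilirubin, add one table that counts subjects by worst post-dose multiple of ULN and, for those High at baseline, by worst post-dose multiple of baseline. The second part is needed because ULN bands alone still hide rises within a band. The protocol's entry limits are one available cut-point; the sponsor should set the final ones. This is for tabulation only and implies no rule for managing subjects.

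Footnote [2] can stay as it is. The cost is SAP and shell wording, a few programmed rows and slightly longer tables. All the data are already collected.
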